
Objective and Purpose

The primary objective of this study is to evaluate the effect of two experimental hops extract-containing dentifrices on gingivitis relative to a positive control 0.454% SnF2 dentifrice and a negative control dentifrice after 12 weeks of product use.

The secondary objective is to assess the effect of two experimental hops extract -containing dentifrices have on gingivitis relative to a positive control 0.454% SnF2 dentifrice and a negative control dentifrice after 4 weeks of product use.

Trial Design

Primary Endpoint

The primary endpoint will be the measurement of the total number of bleeding sites.

Secondary Endpoints

The secondary endpoints will be:

- Percent number of bleeding sites after 4 weeks
- Löe-Silness Gingivitis Index (LSGI) score at 4 and 12 weeks

Trial Design/Type

This is a randomized, four-treatment, parallel-group, double-blind clinical trial. The target population is approximately 120 adult volunteers with mild to moderate gingivitis. At the baseline visit, subjects will undergo a gingivitis assessment using the Löe-Silness Gingivitis Index by a licensed dentist. One hundred twenty (approximately 30 per group) will be randomly assigned to 1 of 4 treatments at baseline. Oral safety and gingival health evaluations will be repeated at 4 weeks and 12 weeks.

Table 1. Study Schedule by Procedure Type and Visit

PROCEDURE	VISIT 1 BASELINE	VISIT 2 WEEK 4	VISIT 3 WEEK 12
Informed Consent	X		
Medical History Review	X	X	X
Inclusion/Exclusion Criteria	X		
Demographics	X		
Concomitant Medications	X	X	X
Urine Pregnancy Test for Females of Child-bearing Potential	X		

Continuance Criteria		X	X
Oral Examination	X	X	X
Löe-Silness Gingivitis Index Evaluation	X	X	X
Adverse Events (AEs)		X	X
Take-home Kit Distribution	X	X	
Take-home Kit Return		X	X
General Comments	X	X	X
Subject Accountability			X

Randomization

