General Comments can be recorded at any time during the study. AEs will be documented in eCRF. Any subject reported AE that remains unresolved by the end of the study should be followed up until resolution by the Investigator/designee. Examiner-observed AEs that are unresolved at the end of the study are followed up to resolution at the discretion of the Medical Monitor. All resolutions should be documented only as source documentation. If a subject is unreachable to determine whether the AE has been resolved, the attempts to contact the subject should be documented as source documentation.

Statistics

Statistical Methods

Summary statistics (*e.g.*, means, standard deviations, frequencies.) of the demographic characteristics will be calculated for each treatment group and overall. Gingivitis scores will be calculated for each treatment group and visit.

Primary Efficacy Analysis

Comparisons to baseline will be investigated using paired-difference t-tests. The treatment groups will be compared using the analysis of covariance method with baseline as a covariate. If normality assumptions are not satisfied, transformation of the data and/or non-parametric analyses may be carried out. Statistical tests for treatment comparisons will be two-sided using a 5% significance level. No adjustment will be made for multiple comparisons. Additional analyses may be performed to fully understand the data.

The following hypotheses will be tested using a serial gatekeeping approach. Using this approach, differences between groups are tested in accordance with a pre-defined hierarchical approach such that the subsequent comparison is statistically tested only if the null hypothesis for the prior test is rejected. The hierarchical approach is detailed below.

For model sensitivity Hypothesis 1 will be tested at Week 12 for the total number of bleeding sites.

Hypothesis 1:

Null: The mean is equal between the Positive Control Group and Negative Control Group.

Alternative: The mean is not equal between the Positive Control Group and Negative Control Group.

If the null hypothesis for Hypothesis 1 is rejected, Hypothesis 2A will be tested at Week 12 for the total number of bleeding sites.

Hypothesis 2A:

Null: The mean is equal between the Experimental Toothpaste #2 Group and Negative Control Group.

Alternative: The mean is not equal between the Experimental Toothpaste #2 and Negative Control Group.

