If the null hypothesis for Hypothesis 2A is rejected, Hypothesis 2B will be tested at Week 12 for the total number of bleeding sites.

Hypothesis 2B:

Null: The mean is equal between the Experimental Toothpaste #1 Group and Negative Control Group.

Alternative: The mean is not equal between the Experimental Toothpaste #1 Group and Negative Control Group.

If the null hypothesis for Hypothesis 2B is rejected, subsequent analyses will compare the experimental groups with the positive control group at Week 12. These analyses will focus on the total number of bleeding sites, consistent with the study's primary objective. Percent number of bleeding sites, LSGI score, Week 4 and Week 12 visits, and all other treatment comparisons will also be analyzed. No adjustment will be made for multiple comparisons.

Safety Analysis

Summary tables will be provided for all reported AEs by MedDRA code and treatment group with safety analysis set. Tables will also be provided for all reported AEs by MedDRA code and subject.

Number of Subjects Planned to Be Enrolled

Power analyses were conducted with $\alpha=0.05$, using a 2-sided test. Up to 120 subjects will be enrolled in the study assuming ~5% dropout rate. Data were utilized from a similarly designed study with the same examiner and endpoints (from 2020054).

Twenty-eight subjects per group completing this trial should provide at least 80% power to detect a difference in number of bleeding sites of at least 8 units between treatments assuming the variability (SD) number of bleeding sites is 10. Assuming the variability (SD) of whole mouth LSGI is 0.1, a sample size of 28 subjects per group should provide at least 80% power to detect a difference in LSGI of at least 0.08 units between treatments.

Level of Significance

The level 0.05 of significance will be used for treatment comparisons.

Termination Criteria

Early termination is not anticipated for this study.

Procedure for Missing, Unused and Spurious Data

Unless noted otherwise, missing data will not be imputed. All analyses will be based on observed data only.

Procedure for Reporting Deviations from the Original Statistical Plan

When differences exist in descriptions or explanations provided in this protocol and the Statistical Analysis Plan (SAP), the SAP takes precedence; the differences will be explained in the clinical study final report.

Subjects to be Included in the Analyses

The following populations are defined for the purpose of the analysis:

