Intent-to-treat (ITT) Population

The ITT population will include all randomized subjects who are confirmed to have received study treatment and have at least one post-treatment efficacy measurement. This will be the primary population for the analysis of efficacy endpoints.

Per Protocol (PP): All subjects who received study treatments and completed the study per protocol (also known as “evaluable population”).

Safety Analysis Set: All subjects who received study treatments and had oral examinations conducted will be included.

Direct Access to Source Data/Documents

The Investigator has the responsibility for ensuring that all source documents (*i.e.*, study and/or medical records) and CRFs are completed and maintained according to the study protocol and local regulations and are available at the site. Any CRF used as a source document must be identified as such in the Investigator Notebook.

The Data Manager will supply the paper and/or eCRFs to be used in this study. It is the responsibility of the Investigator to maintain and submit accurate and timely CRFs to the Sponsor. All hard copy CRFs will be filled out legibly in ink.

All questions should be answered. For paper CRFs, if an entry requires correction, a single line will be placed through the entry so as not to obscure the original record, the corrected entry will be initialled and dated by the individual making the change, and a reason will be given for the change. There will be no whiteouts or erasures. For eCRFs, if an entry requires correction, the change is made directly to the CRF in the database, the user is prompted to provide a reason for the change, and the correction is logged in by an electronic audit trail.

As necessary, the Data Manager may make specified allowable changes to the database without issuing a query to the site, as agreed upon by study site staff per this protocol. Examples of allowable changes include incorrect date formats, incorrect current year recorded (as in the start of a new year), and unambiguous spelling errors. Changes to common abbreviations and symbols to equivalent text to meet system or coding constraints (*e.g.*, @ = at, ~ = approximately), may also be allowable. Values that are ambiguous or open to interpretation will be queried to the sites' staff. It is the responsibility of the Data Manager to ensure all changes are supported by information contained elsewhere and/or are unambiguous.

Quality Assurance and Quality Control

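### Subjects seen at Week 4 but not at Week 12 are in the ITT population yet contribute nothing to the gated Week 12 tests, which in effect analyse only subjects observed at Week 12

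*Combined protocol and SAP*

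**What the plan says.** All references are to the combined protocol and SAP.

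- **Population.** Under *Subjects to be Included in the Analyses*, the ITT population is the randomized subjects with confirmed treatment who "have at least one post-treatment efficacy measurement. This will be the primary population for the analysis of efficacy endpoints".
- **Visits.** Under *Trial Design/Type*: "Oral safety and gingival health evaluations will be repeated at 4 weeks and 12 weeks". One post-treatment score can therefore be a Week 4 score.
- **Primary test.** Under *Primary Efficacy Analysis*: "The treatment groups will be compared using the analysis of covariance method with baseline as a covariate". The first gate is explicit about timing: "For model sensitivity Hypothesis 1 will be tested at Week 12 for the total number of bleeding sites". Hypotheses 2A and 2B, and the later comparisons with the positive control, are also placed at Week 12.
- **Missing data.** Under *Procedure for Missing, Unused and Spurious Data*, unless noted otherwise, "missing data will not be imputed. All analyses will be based on observed data only".
- **Sample size.** Under *Number of Subjects Planned to Be Enrolled*: "Up to 120 subjects will be enrolled in the study assuming ~5% dropout rate". Power is stated for 28 completers per group, a difference of 8 bleeding sites and an SD of 10.

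The supplied text contains no repeated-measures model, carry-forward rule or missing-data sensitivity analysis.

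**The concern.** An ANCOVA of the Week 12 count on baseline needs a Week 12 count. Without imputation, a subject whose only follow-up score is from Week 4 has no outcome in that model. The subject is counted in the primary population but is absent from every step of the gated sequence. The set actually tested is subjects observed at Week 12, which the plan does not name.

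At stake is the Week 12 contrast. If loss after Week 4 is related to how a subject was responding, and differs between arms, the observed-case difference is biased even though the Week 4 score that could correct for it is in the database. Hypothesis 1 gates the hops comparisons, and the negative control is the reference in Hypotheses 1, 2A and 2B. Selective loss of poor responders from that one arm would shrink all three differences together.

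**Working it through.** **1. The plan's own power figure.** With n = 28 per group, difference 8 and SD 10, SE = 10 × √(2/28) = 2.67 and 8/2.67 = 2.99. The noncentral t gives 83.6% power (84.9% by normal approximation), and 26 per group would give 80%. The claim of at least 80% is correct. For enrolment, 4 × 28 = 112 and 112/0.95 = 118, consistent with 120.

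**2. How many subjects are affected.** Planned loss is 120 × 0.05 = 6, so 114 subjects have Week 12 data, or 28.5 per arm. The documents do not split dropout before and after Week 4. If a fraction f of the 6 has a Week 4 score, the ITT population numbers 114 + 6f:

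| f (assumed) | ITT population | In the Week 12 ANCOVA | In ITT but not in the gated tests |
|---|---|---|---|
| 0 | 114 | 114 | 0 |
| 0.5 | 117 | 114 | 3 |
| 1 | 120 | 114 | 6 |

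Because 28.5 per arm is no fewer than the 28 completers used for power, planned power is intact.

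**3. What selective loss would do.** From the plan: 30 per arm, SD 10 and difference 8. Assumed: SD 10 is the baseline-adjusted SD, the Week 4-Week 12 correlation is 0.7, all losses occur after Week 4, and the odds of loss rise e-fold per SD of worse Week 4 score. The difference is negative control minus comparator.

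If m of n subjects in an arm are lost, and their mean Week 4 score is s SDs worse than the arm's, the observed Week 12 mean of that arm falls by

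[m/(n − m)] × 0.7 × 10 × s.

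For n = 30 this is 0.24s for m = 1, 0.50s for m = 2 and 0.78s for m = 3. Simulation gives a shift of about 0.70 for m = 3, so s is about 0.70/0.78 = 0.9. The shifts are then about 0.22, 0.45 and 0.70.

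| Lost after Week 4 | Arithmetic | Simulated estimate | Power or type I error |
|---|---|---|---|
| None | 8 | 8.0 | power 86% |
| 2 control, 1 comparator | 8 − 0.45 + 0.22 = 7.77 | 7.74 to 7.77 | power 82% |
| 3 control, 0 comparator | 8 − 0.70 = 7.30 | 7.30 to 7.36 | power 78% |
| 0 control, 3 comparator (true difference 0) | 0 + 0.70 | about +0.7 | type I error about 6% |
| Equal in both arms | shifts cancel | 8.0 | no bias |

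Check of the fourth row: SE = 10 × √(1/27 + 1/30) = 2.65 and 0.70/2.65 = 0.26 SE. Then P(|Z + 0.26| > 1.96) is about 5.8%.

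In the third row, 27 against 30 subjects with no bias would give 84% power. About 2 of the 8 points lost (86% to 78%) are therefore sample size alone.

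**4. Effect of using Week 4.** In the third-row scenario, a likelihood estimate that uses the Week 4 score gives 7.96 to 8.03 against a true 8.

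**The case against.** The strongest reply is that the plan has made a coherent choice. There is one ITT definition, it serves several efficacy endpoints including those at Week 4, and an observed-data rule is laid over it. A reader might infer that two definitions of the primary population contradict each other; the text does not support that. Nor are the Week 4 scores discarded: these subjects enter the Week 4 analyses, and their data are only not used for Week 12.

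A reader might also infer that the trial is underpowered or the primary result unsound. The documents do not show this either. Power already rests on completers. Only the 3-0 stress case falls below 80%: halving the selection slope gives 7.63 sites and 81%, and lowering the correlation to 0.4 gives 7.66 and 81.5%. A more extreme case, all 6 losses in one treated arm, gives a bias of about +1.4 and type I error of about 8%. But under equal risk, 6 losses fall in one named arm with probability 0.25^6, about 0.0002. The listed discontinuation reasons do not name lack of efficacy, so response-driven loss is an assumption.

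Finally, the simulated loss depends only on the observed Week 4 score, which is the condition a likelihood model needs. Its near-perfect recovery is therefore largely built in. Loss driven by later events, such as adverse events or antibiotic use, was not tested.

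All of this limits the size of the point. It does not remove the gap. The *unless noted otherwise* clause and SAP precedence leave room for a rule, but none is supplied, and permission for additional analyses is not prespecification. Withdrawn subjects are not replaced, and *Subject Continuance Criteria* allows exclusion from the analysis, so missing Week 12 data could exceed simple dropout.

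**Conclusion.** The point stands as an inexpensive improvement to the primary analysis, not as a demonstrated threat to the result. The Week 12 tests cannot use ITT subjects who have only a Week 4 score, so they are in effect analyses of subjects observed at Week 12.

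At planned dropout, 0 to about 6 of 120 subjects are affected and planned power holds. Bias requires loss after Week 4 that both depends on response and differs between arms. Under the assumptions above it is about 0.2 to 0.3 sites for a 2-1 split and about 0.7 for a 3-0 split, against a design difference of 8, and zero for balanced loss. The correlation, the selection strength and the imbalance are assumed; none is given in the documents.

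**What to change.** Make the primary analysis a likelihood-based repeated-measures model (MMRM) for the number of bleeding sites at Weeks 4 and 12. Include treatment, visit, treatment-by-visit, baseline and baseline-by-visit, with unstructured within-subject covariance. Test Hypotheses 1, 2A and 2B on its Week 12 contrasts in the same order. The model uses every ITT subject with a baseline and either follow-up visit, needs no imputation and so fits the observed-data rule, and supplies the Week 4 contrast for bleeding sites from the same fit. With complete data the Week 12 contrast is essentially that of the ANCOVA.

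Keep the Week 12 ANCOVA as a sensitivity analysis, labelled as subjects observed at Week 12. At the least, the plan should name the Week 12 analysis set and say how Week-4-only subjects are handled.

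The cost is protocol and SAP wording, slightly more programming and a few extra covariance parameters, with no new visits, data or subjects. The model corrects only for loss explained by baseline and Week 4 scores. If dropout is low and balanced, its results will be close to the ANCOVA.
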